Logistic Regression and Elastic Net Regularization for the Diagnosis of Fibromyalgia: A Quantitative approach using B-mode Ultrasound

Authors:

[name]^{1,3}, MSc, B.Eng; [name]^{1,3}BSc.; [name]^{1,2}, MSc (C), B.Eng; [name]^{1,2,3} MD, PhD, FRCPC, FAAPMR

¹University Health Network – Toronto Rehabilitation Institute, Toronto, Ontario, Canada

²Institute of Biomaterials and Biomedical Engineering (IBBME), University of Toronto, Toronto, Ontario, Canada

³Department of Medicine, Division of Physical Medicine and Rehabilitation, University of Toronto, Toronto, Ontario, Canada

Date: September 9th, 2019

Corresponding Author:

[name], PhD, FRCPC, FRCPC, FAAPMR

Associate Professor, Department of Medicine

Division of Physical Medicine and Rehabilitation

University of Toronto

Toronto Rehabilitation Institute

[name]

[name]

P: [contact] [name]

Email: [contact]

Abstract

Background: Fibromyalgia (FM) is a chronic widespread pain disorder characterized by widespread tenderness, psychological distress, fatigue, and sleep disturbance. The cause of FM continues to be unknown. Current methods of fibromyalgia (FM) diagnosis remains a challenge for clinicians due to a lack of objective diagnostic tools. One proposed solution is the use of quantitative ultrasound (US) techniques, such as image texture analysis, which has demonstrated discriminatory capabilities with other chronic pain conditions like Myofascial Pain Syndrome (MPS). We propose the use of US image texture variables to construct an elastic net regularized, logistic regression model, for differentiating between the trapezius muscle in the healthy and FM patients.

Methods: Ethical approval has been obtained from the University Health Network (UHN) Research Ethics Board. This proposed study is a diagnostic case-control study with one major independent binary outcome measure (FM present or Healthy), to create 2 patient cohort groups. Ultrasound imaging data will be collected from both cohorts and the image texture variables will be used to construct predictive logistic regression models.

Discussion: This will be the first study that assesses the discriminative capabilities of B-mode ultrasound image texture of healthy muscles and muscles with FM present. Findings from this study will allow further research into diagnostic modelling for FM.

Keywords: Ultrasound, Imaging, Logistic, Regression, Fibromyalgia, Regularization

List of Abbreviations:

US: Ultrasound

FM: Fibromyalgia

MPS: Myofascial pain syndrome

MTrP: Myofascial trigger points

LASSO: Least absolute shrinkage and selection operator

Background

Fibromyalgia (FM) is a chronic widespread pain disorder characterized by widespread tenderness, psychological distress, fatigue, and sleep disturbance¹. It has an estimated prevalence of 1.1-6.4% of the general population². In the United States, greater disease burden has been reported in FM patients which involve poorer health status, function, sleep, lower productivity, pain-related medications, increased comorbidities and higher costs³. The cause of FM continues to be unknown. The current clinical method of diagnosis of FM is by applying the 2016 FM criteria^{4,5}. These are subjective and do not require a physical examination. Therefore, subjectivity is present when diagnosing FM.

Another method to diagnose FM could be to create a diagnostic biomarker that is objective, reliable and based on the underlying pathophysiology. A biomarker is a characteristic that can be measured objectively to indicate the underlying pathophysiological process⁶. The FDA has identified that qualified biomarkers are one of the following: diagnostic, prognostic, predictive, and pharmacodynamic. “A diagnostic biomarker is a disease characteristic that categorizes a person by the presence or absence of a specific physiological or pathophysiological state or disease”. Our study was designed to create a diagnostic biomarker that could be feasible for clinical utilization and assist in reducing subjectivity and heterogeneity when combined with the current clinical criteria⁴.

From an imaging perspective, there is very little literature available. Magnetic resonance imaging of the muscles in FM patients have been studied in the past which did not show any significant abnormality⁷. Ultrasonography (US) has also been used to study the trigger points found on the outer aspect of the greater trochanter in FM patients⁸. Similarly, this study did not show any significant abnormalities in FM patients. However, the study was limited due to a

small sample size and the absence of a healthy control group. Currently, no study exists to compare FM patients and healthy controls using clinical findings and quantitative US.

Rationale for Utilization of Quantitative Ultrasound

There is evidence in the literature for altered nociception in patients with FM⁹. FM is also characterized by heightened pain sensitivity to sensory stimuli, possibly as a result of the changes in the central processing in the brain, referred to as central sensitization¹. From a mechanistic perspective, the abnormal efferent activity could be reflected in the affected skeletal muscle. Our study objective is to explore this possibility using image texture feature analysis in B-mode US imaging. We believe that this may be possible since we have previously shown that texture features can not only discriminate between healthy controls and patients with neck pain but also between the two clinical phenotypes of Myofascial Pain Syndrome (MPS), namely groups that contain latent and active myofascial trigger points (MTrPs)¹⁰. Towards this, we propose to use the image texture features to construct a regularized logistic regression model in order to predict and discriminate between healthy controls and fibromyalgia affected muscle.

To summarize, our specific research questions are as follows:

- a. Can a regularized logistic regression model, built on texture variables extracted from B-mode ultrasound images of the upper trapezius discriminate between healthy, and FM subjects? Our hypothesis is that the model should effectively differentiate the two cohorts due to our previous work/success with other chronic pain disorders (MPS).
- b. How does regularization impact the overall performance of the trained model? Our hypothesis is that it should improve its generalizability.
- c. Does the holdout, test data validate the predicted performance of the logistic regression model? Our hypothesis is that it will be within 1 standard error of the prediction mean.

Methods & Design

Study Design:

The study conforms to the Consolidated Standards of Reporting Trials recommendations.

Ethical approval is approved by the University Health Network (UHN) Research Ethics Board.

This study is registered under the National Institutes of Health ClinicalTrials.gov. This proposed study is a diagnostic case-control study with one major independent binary outcome measure (FM present or Healthy), to create 2 patient cohort groups.

Participants:

Recruitment

Study participants will be recruited from the MSK/pain specialty outpatient clinic at the Toronto Rehabilitation Institute. Toronto Rehabilitation institute is the largest rehabilitation hospital in Canada, owned and operated by the University Health Network (UHN). The recruitment procedures will run in line with the approved guidelines from the UHN research ethics boards. Informed consent was obtained from each participant. Participants will not be coerced into participating and will be informed that they have the right to withdraw at any time during the experimental procedures. They will also be informed they have the right to withdraw their data prior to publication. Participants will be briefed and consented on recruitment prior to commencing the study procedures.

Eligibility Criteria

A specialist in physical medicine and rehabilitation with 25 years of experience ([name]) will perform the standardized physical assessment on consecutive patients referred to the clinic. Female or male participants who meet the following inclusion criteria will be included in the study as FM participants: (1) chronic widespread pain, (2) fitting the 2016 FM criteria, (3)

absence of myofascial pain syndrome trigger points, (4) participants agree to sign a consent to volunteer for the research, and (5) between the ages of 20 and 65 years (44.3 ± 13.9 years). Age matched healthy controls with no past medical history were also collected.

Exclusion Criteria

Participants were excluded if they demonstrated clinical evidence of another cause for widespread pain, such as: (1) polymyositis, (2) dermatomyositis, (3) endocrine disorders, etc. Additionally, no participants will be recruited that have performed any physical exercise up to three days prior to entry into the study.

Experimental Protocol

Data Acquisition

The experimental protocol will be carried out in the MSK/pain specialty outpatient clinic at Toronto Rehabilitation Institute. Following the completion of the preliminary intake forms and participant debriefing, informed consent will be obtained. Each participant will be seated upright with their hands comfortably on their thighs in a chair that has a high supportive back. They will be asked to relax their neck and shoulder muscles. [name] will then apply the inclusion and exclusion criteria to the patient and assess entry into the study. A research associate, blinded to the clinical status of the study participant, will collect the ultrasound images using a Sonosite X-porte ultrasound system (SonoSite Canada Inc. c/o Visualsonics, [name]) at a depth of 3.0 cm or less and with a linear ultrasonic transducer of 6-15 MHz. The image settings such as depth, sector size, and time gain compensation (TGC), will be kept constant for all participants. The transducer will then be placed perpendicular on the upper trapezius muscle on each side, and its angle was adjusted to acquire the highest quality image. Ultrasound Gel will be used to coat the entire surface of the

transducer before it touched the skin surface. The location on the muscle will be standardized across study participants by being at the midpoint of the muscle belly between the C7 spinous process and the acromioclavicular joint. From that position, the transducer will be moved at a speed of approximately 1 cm/sec toward the acromioclavicular joint to obtain a 10-sec video. One video will be acquired from each side of the muscle group per participant.

Image Pre-processing

All images pre- and post-processing will be performed with MATLAB and the image processing toolbox¹¹. Images will be visually and statistically inspected for quality based on image intensity, contrast, and ability to discriminate muscle fibers. This is necessary to maintain a high standard of imaging data quality, and suspect no more than 15% of the data should be removed due to constraints. Next, since we are analyzing ROI's in the muscle we must extract only a certain number of frames from each video series. We will achieve this using an image filtering method that has been previously used by our group called the CW-SSIM¹² filtering method¹³. It will be used to objectively calculate and extract image frames from each video series in order to obtain the maximal number of images, while still maintaining uniqueness (minimal image overlap). After this procedure is finished we will extract a rectangular ROI estimation of the upper trapezius muscle excluding the upper and lower fascial borders. Lastly, the images will be labelled and organized for further processing.

Feature Extraction

Texture variables will then be extracted from the image ROI's using MATLAB and the image processing toolbox. The features to be extracted are as follows:

1. First order histogram parameters associated with image grayscale. These include mean, standard deviation, skewness, and kurtosis.

2. Gray level co-occurrence matrices (GLCM)¹⁴ will be calculated utilizing 4 directions (0,45,90,135 degrees). 76 variables are then created.
3. Lastly run-length parameters¹⁵ will be determined by gray level run-length matrices based upon the four given directions. Averaging the directions together gives seven features.

In total 88 feature variables will be extracted from each ROI, providing a feature descriptor dataset.

Elastic Net Regularized Logistic Regression

We will then construct and train an elastic net regularized logistic regression model on the dataset using the binary class labels constructed earlier¹⁶. This will be done using MATLAB and the Statistics and Machine Learning Toolbox¹⁷ and performed on a train/test split (80/20) of the original training data. The model will be regularized using the elastic net, which will improve the generalizability of the classification model on unseen data (avoid overfitting problems). The elastic net penalization method also provides a form of variable selection helping to minimize the effect of rank deficiency.

Model Validation

The model will be validated using 10-fold nested cross validation on the training data due to the fact the model needs hyper-parameter tuning alongside the validation process. This requires a nested procedure where the hyper-parameter tuning is done in an inner loop and the validation of the model is in an outer loop. This will allow for an optimized, trained model that should generalize well to unseen data. This generalization will be tested using the final holdout set and will either confirm or deny whether the constructed model is a good classifier for this task.

Results

After the methodology is applied to all training data, performance metrics can be extracted from the results to demonstrate the model efficacy. Performance metrics like sensitivity, specificity, area under the curve (AUC) and accuracy will be extracted in order to characterize the model performance. These metrics will be averaged across the 10-folds (mean + stdev), and these values will be compared to the final metrics extracted from the holdout test set. If the test set values fall within 1 stdev, it will confirm the accuracy of the performance estimation during the training.

Primary Outcome

The primary outcome measures:

1. Binary classifier discriminates effectively (>70 % accuracy) between the healthy and muscle with FM.
2. Impact of regularization on the model performance.
3. Holdout test validation of the predicted performance.

Discussion

The overarching goal of our research utilizing image texture features is to eventually provide diagnostic aid to clinicians through the usage of clinically feasible, objective and reliable quantitative ultrasound techniques. While computer aided diagnosis research in ultrasound has been heavily explored in areas such as cancer and liver diseases¹⁸⁻²⁰, there has been little to no work in chronic pain¹³. This is the basis for this project proposal utilizing logistic regression modeling with elastic net regularization; the objective is to develop a statistical model with good predictive and diagnostic capabilities.

We are using logistic regression as our classification model due to its efficiency, computational resource requirement, interpretability, input feature scaling invariance, and ease of regularization²¹. The fact that logistic regression intrinsically calculates the predictive probability is a major strength of the model, as other classification techniques require further computationally intensive cross-validation to achieve this.

Regularization is a specific technique that is often used as a remedy to solve overfitting in classification models for machine learning²². In a general sense, regularization techniques are used to reduce a model's predictive error on unseen data by minimizing model variance with a given training set by smoothing the predictions. This is done by constraining (regularizing) the regression coefficients towards zero which discourage overly complex (flexible) models. What must be noted is that regularization does not improve the performance of the model on the data it was trained on. More intuitively, regularization acts as a penalty against complexity and steers the model away from memorizing (overfitting) the dataset. For this protocol we are utilizing elastic net regularization (a well-known technique) to improve the performance against the unseen data.

Until now, the literature shows that the diagnosis of FM remains challenging, in part due to its non-specific symptoms, which overlap with many other disorders such as myofascial pain syndrome. Even though patients who present symptoms such as chronic widespread pain, emotional distress, cognitive and sleep disturbances may be formally diagnosed with FM, it is possible that their primary disorder is not FM and has an entirely different pathophysiological mechanism. This protocol should demonstrate the effectiveness of texture analysis techniques when differentiating between FM patients and healthy individuals. Post-image acquisition texture analyses may provide some insight into the pathophysiology underlying FM.

Limitations and Conclusions

Our study has limitations and one of them concerns the generalizability of our findings, since we are evaluating images of the upper trapezius for patients and healthy participants. The upper trapezius muscles may not be representative of the whole patient or the differences between patients who have varying symptomatology and areas of pain. Further research is needed to replicate our findings using muscle groups other than the upper trapezius. We plan to conduct these studies and to correlate our findings with the extent of central sensitization. Another potential limitation is the amount of healthy control recruits available. It is difficult to find participants that do not possess stiffness and myofascial trigger points in their upper trapezius muscle, even among seemingly healthy populations. We suspect this may limit our numbers for this group and fully expect to deal with an unbalanced dataset. There are many methods of compensating for this discrepancy during model construction, training and statistical analysis and will employ them as needed.

In conclusion this study should provide an effective, discriminatory classifier trained on B-mode ultrasound images that can differentiate between healthy muscle and muscle with FM in the upper trapezius. This is one more step in our overarching goal of providing increasingly objective diagnostic tools for clinicians when diagnosing chronic pain disorders.

Acknowledgements: N/A

Declarations

Ethics approval and consent to participate:

Informed consent will be obtained from all subjects participating in this study. Ethical approval was approved by the University Health Network (UHN) Research Ethics Board (Approval

Number: 15-9488.8). The approval form is included in the supplementary files of this submission. This study is registered under the National Institutes of Health ClinicalTrials.gov.

Consent for publication:

Not applicable.

Availability of data and material:

The datasets used and/or analyzed during the study will be available from the corresponding author upon reasonable request.

Data Monitoring Committee

A DMC is not applicable for this study since it is not a multi-location study.

Trial Status:

Protocol version and date: Version 1, Sept. 10, 2019

Recruitment: Completed Sept. 6, 2019

Competing interests:

The authors declare that they have no competing interests.

Funding:

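### The protocol judges the holdout result by 1 standard error in research question c and by 1 standard deviation in Results, and does not reconcile the two

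*Protocol*

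**What the plan says.** Research question c (Protocol, end of Rationale for Utilization of Quantitative Ultrasound) asks "Does the holdout, test data validate the predicted performance of the logistic regression model" and attaches a numerical expectation: "Our hypothesis is that it will be within 1 standard error of the prediction mean". It gives no formula for the standard error.

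The Results section summarises sensitivity, specificity, AUC and accuracy over the ten folds by their mean and standard deviation. It then says that "these values will be compared to the final metrics extracted from the holdout test set", and gives the rule: "If the test set values fall within 1 stdev, it will confirm the accuracy of the performance estimation during the training".

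The Primary Outcome section lists as item 3 "Holdout test validation of the predicted performance", with no threshold. The only numerical yardsticks for that outcome are therefore the two statements above. Nothing in the protocol equates the two terms or says which one decides.

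**The concern.** The standard deviation over ten folds describes the spread of single-fold results. The standard error of their mean is ordinarily that figure divided by the square root of ten. The two bands are nested, so any result within 1 SE is also within 1 SD, but the reverse does not hold. A holdout result could therefore be declared confirmatory under Results while failing the hypothesis in question c, on the same data and for a listed primary outcome.

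A second issue does not depend on how the term is read. Results treats falling inside the band as confirmation that the performance estimate is accurate. In a small sample, a holdout set that performs materially worse can still fall inside it.

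**Working it through.** **Inputs from the protocol.** Ten outer folds (Model Validation); 80/20 split (Elastic Net Regularized Logistic Regression); fold mean and SD compared with the holdout (Results). The protocol gives no figure of its own to reproduce.

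**Assumptions.** No sample size is stated, so N is varied from 50 to 1000. Units are independent, the folds share 80% of the data (8% each), the holdout is the other 20%, and overlap between the cross-validation training sets is ignored. The metric is accuracy alone. SE is taken as fold SD / sqrt(10).

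**Step 1: relative width.** SD / SE = sqrt(10) = 3.16. This needs no assumption about N.

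**Step 2: pass rates when performance is truly equal.** With per-unit variance v:
- fold SD = sqrt(v / 0.08N) = sqrt(12.5 v/N)
- SE = sqrt(1.25 v/N)
- SD of holdout minus fold mean = sqrt(v / 0.2N + v / 0.8N) = sqrt(6.25 v/N)

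Band divided by the SD of the difference is sqrt(1.25/6.25) = 0.447 for the SE rule and sqrt(12.5/6.25) = 1.414 for the SD rule. Referred to a t distribution with 9 degrees of freedom, because the SD is estimated from ten folds, these give pass probabilities of 33.5% and 80.9%. The gap is 47.4 percentage points.

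**Step 3: binomial simulation** (400,000 repetitions per setting).

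| Assumed N | 50 | 100 | 200 | 400 | 1000 |
|---|---|---|---|---|---|
| 80% in both: within 1 SE | 34.1% | 34.0% | 33.6% | 33.6% | 33.4% |
| 80% in both: within 1 SD | 81.1% | 81.1% | 81.2% | 81.0% | 81.0% |
| 80% in both: within 1 SD only | 47.0% | 47.1% | 47.6% | 47.4% | 47.6% |
| Holdout truly 70%: within 1 SD | 68.7% | 60.9% | 48.7% | 30.1% | 6.4% |
| Holdout truly 70%: within 1 SE | 27.7% | 22.7% | 15.2% | 6.9% | 0.7% |

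If the standard error was meant as the fold SD, the third row is 0% throughout.

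**Step 4: band widths at an assumed N = 100, accuracy 80%.** The simulated bands average +/-4.4 points (SE) and +/-13.8 points (SD). The holdout's own sampling SD is sqrt(0.16/20) = 8.9 points. The SD of the holdout-minus-fold-mean difference is sqrt(6.25 x 0.16/100) = 10.0 points. The SE band is narrower than both figures and the SD band is wider than both.

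**Step 5: hand check of the 61%.** With 80% in the folds and 70% in the holdout, the SD of the difference is sqrt(0.16/80 + 0.21/20) = 11.2 points, around a mean of -10. The chance of falling within +/-13.8 is about Phi(3.8/11.2) - Phi(-23.8/11.2) = 0.633 - 0.017 = 0.62, in line with the simulation.

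**The case against.** The strongest reply is that the two statements play different roles. Question c voices an expectation, while Results alone gives a procedure that can be computed and a decision rule. An analyst would have one workable rule, and meeting it while missing a hypothesis is a possible outcome rather than a contradiction. The standard error may also be loose wording for the fold SD. That reading stays open and makes the consequence conditional. It does not remove the defect: the protocol does not assign those roles, and question c attaches its own number to the validation question.

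Three further points limit the size of the concern.
- The rates cover accuracy alone, whereas Results refers to several metrics. If sensitivity, specificity and accuracy all had to pass (balanced classes, all at 80%, independent units, N = 100 to 1000), the pass rates would be about 62% under SD and 10% under SE.
- The 20% holdout is inferred, because the split is described as one of the original training data. Units are also unlikely to be independent: "One video will be acquired from each side of the muscle group per participant", and frames are then extracted "in order to obtain the maximal number of images". These points could change the rates but not the factor of 3.16.
- The >70% accuracy target in primary outcome 1 is unaffected.

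A reader might infer that the SD band is too narrow because its formula omits the holdout's sampling error. The figures do not support that: each fold is smaller than the holdout, so the SD band (13.8 points) exceeds the SD of the full difference (10.0). The narrowness applies to the SE band only.

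A reader might also infer, from recruitment having been completed just before the protocol date, that the yardstick was chosen after the holdout had been seen. The protocol does not show whether the holdout had been opened.

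**Conclusion.** The mismatch is real and lies in current text. It concerns the only thresholds given for a listed primary outcome, so it is a conflict within the protocol rather than detail left to an analysis plan. Its consequence depends on the undefined term. If SE means SD / sqrt(10), about 47-48% of holdout results under truly equal accuracy would satisfy Results and miss the hypothesis. If the term was loose, none would, and the correction is a single term. It would go too far to say that the protocol certainly contains two rival rules giving opposite verdicts.

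The claim of confirmation is too strong in a small sample on either reading. At an assumed N = 100, a true 10-point loss passes the 1-SD rule about 61% of the time. Nor is the SD rule without value: at N = 1000 the same loss passes only about 6% of the time. All rates are illustrative and rest on the independence, split and accuracy-only assumptions above; the ratio of 3.16 rests only on the ten folds and the SD / sqrt(10) reading.

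**What to change.** Before the holdout is opened:

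1. State one criterion in identical words in research question c and Results. Name the quantity (fold SD, or SE with its formula) and the metric or metrics it applies to. If several metrics apply, say whether all must pass. If the standard error was loose wording, changing that term settles this step apart from the metrics.
2. In Results, say that a holdout value inside the band is consistent with the cross-validated estimate, rather than that it confirms its accuracy.
3. Report holdout performance and the holdout-minus-cross-validation difference with 95% intervals computed at participant level, since each participant contributes two videos and several frames. Present them as estimates. No coverage is claimed here for any particular interval method, because the check ignored the overlap of cross-validation training sets.

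The cost is wording in two places and one added interval, with no new data. The conclusion becomes weaker than a claim of confirmation, and the interval will be wide if the sample is small. On the idealised assumptions above, with 80% accuracy in both sets, its half-width is roughly 1.96 x 10.0 = 19.6 points at N = 100. At N = 1000 it is 1.96 x sqrt(6.25 x 0.16/1000) = 6.2 points.

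### Controls were screened for any past medical history and FM cases were not, so accuracy above 70% cannot by itself be attributed to FM muscle

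*Protocol*

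**What the plan says.** Eligibility Criteria (Methods & Design) describes the comparison group in one sentence: "Age matched healthy controls with no past medical history were also collected". Age is the only matching variable named.

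FM cases must have chronic widespread pain, meet the 2016 criteria, consent, be aged 20 to 65, and show "absence of myofascial pain syndrome trigger points". Exclusion Criteria adds: "Participants were excluded if they demonstrated clinical evidence of another cause for widespread pain". It names polymyositis, dermatomyositis and endocrine disorders, leaves the list open, and bars physical exercise in the three days before entry.

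The Background lists among the burdens of FM "pain-related medications, increased comorbidities and higher costs".

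Feature Extraction limits the model inputs to image texture: "In total 88 feature variables will be extracted from each ROI, providing a feature descriptor dataset". The first primary outcome is "Binary classifier discriminates effectively (>70 % accuracy) between the healthy and muscle with FM". Limitations and Conclusions expects an "effective, discriminatory classifier trained on B-mode ultrasound images that can differentiate between healthy muscle and muscle with FM". The limitations given there are the single muscle site and the shortage of controls; unequal health screening is not among them.

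**The concern.** The two groups passed through different general-health filters. A history of treated hypertension, for example, would bar a control but not a case, provided it was not thought to explain the pain. Since the Background says that comorbidity and pain medication are raised in FM, the control rule sets close to zero in one group something the protocol expects to be elevated in the other.

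If comorbidity, or the drugs taken for it, leaves any trace in trapezius texture, the classifier can use that trace. The planned reading would credit the whole result to FM in the muscle. At stake is the interpretation of the first primary outcome and of the diagnostic biomarker named as the aim in the Background.

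**Working it through.** **Nothing to reproduce.** The 70% threshold is stated without derivation, and the protocol gives no sample size or class ratio.

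**Can the planned validation detect the problem?** The holdout is a 20% split of the same data, and the nested 10-fold cross-validation runs on the training part. Every fold and the holdout therefore contain cases and controls chosen under the same unequal rules. Agreement between them shows stable performance on these two groups, not what drives it. Blinding of the research associate (Data Acquisition) guards image acquisition, not who was eligible.

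**How much could comorbidity contribute?** Suppose texture carries no FM signal and only marks comorbidity.

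- *c*: share of FM cases with comorbidity or medication. Not in the protocol; assumed, varied from 0 to 1.
- Share of controls with it: 0, from the control rule.
- *se*, *sp*: sensitivity and specificity of texture as a marker of comorbidity. Not in the protocol; assumed.
- *w*: share of participants with FM. Not given; the protocol says only "We suspect this may limit our numbers for this group and fully expect to deal with an unbalanced dataset". Taken as 0.5 and 0.6.

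Accuracy = w·[c·se + (1−c)·(1−sp)] + (1−w)·sp.

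With w = 0.5 this reduces to 0.5 + 0.5·c·(se + sp − 1). Setting it to 0.70 gives c = 0.4/(se + sp − 1). With w = 0.6 the full formula is solved in the same way.

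| se / sp | c giving 70%, w = 0.5 | c giving 70%, w = 0.6 |
|---|---|---|
| 1.0 / 1.0 | 0.40 | 0.50 |
| 0.9 / 0.9 | 0.50 | 0.58 |
| 0.8 / 0.9 | 0.57 | 0.67 |
| 0.8 / 0.8 | 0.67 | 0.72 |
| 0.7 / 0.8 | 0.80 | 0.87 |
| 0.7 / 0.7 | 1.00 | 1.00 |

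The plan requires more than 70%, so c must exceed the tabled value; in the last row that is impossible. At w = 0.5 and c = 0.7, accuracy is 85% for a perfect marker, 74.5% at 0.8/0.9 and 64% at 0.7/0.7.

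**Is the unequal filter the cause?** If controls had the same prevalence c and w = 0.5, accuracy = 0.5·[c·se + (1−c)(1−sp)] + 0.5·[c(1−se) + (1−c)·sp] = 0.5·[c + (1−c)] = 50%, whatever c, se and sp are. In this illustration the route past 70% exists only because prevalence differs between groups.

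A larger FM share is not a useful scenario. At w = 0.7, calling everyone FM scores 0.7·1 + 0.3·0 = 70% with no marker at all. That is a weakness of raw accuracy under imbalance and a separate matter.

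**The case against.** **The design is declared.** Study Design announces a case-control comparison of FM with healthy people, and the conclusion calls the work one more step. Healthy controls are a legitimate first choice. This stands: the fault is the unequal filter combined with an FM-specific reading, not the use of healthy controls.

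**Cases are not unrestricted.** A reader might infer that cases may carry any comorbidity, diabetes included. The text does not support that. Endocrine disorders are a named exclusion, so diabetes is eligible at most on one reading, and trigger points are barred. Limitations and Conclusions implies that controls also had to be free of trigger points, so that criterion does not create the asymmetry.

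**The mechanism is assumed.** Nothing in the protocol shows that comorbidity or pain medication alters trapezius texture. This stands, and it is why no bias can be quantified. The Rationale section does report that texture separates controls from neck-pain patients and distinguishes latent from active trigger points. On the protocol's own account, then, texture responds to conditions other than FM.

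**Reporting may be left to the statistical analysis plan.** Tables by group and subset analyses often are, and their absence here is not the complaint. The eligibility rule and the reading of the result are fixed in the protocol.

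**Conclusion.** The concern holds in a limited form. Comorbidity and medication are confounded with group by the eligibility rules, and no planned step matches, adjusts for or acknowledges this. A result above 70% therefore supports discrimination of FM patients from people with no past medical history. Attribution to FM muscle needs more.

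A reader might go further and infer that the classifier will reach 70% by detecting ill-health. The protocol does not support that: it gives neither the prevalence of comorbidity in cases nor its effect on texture. The 40% figure is a bound that assumes a perfect marker and no FM signal, and it weakens quickly as the marker becomes less accurate. The direction of the risk is clear; its size is unknown.

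**What to change.** Leave the eligibility text unchanged. Trial Status records recruitment as completed on Sept. 6, 2019, so rewriting the control rule would alter no participant and would misdescribe how controls were chosen. Nor would applying the case exclusions to controls equalise comorbidity, given what the Background says about FM.

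Instead:

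1. Report comorbidity and pain medication by group.
2. Fix in advance a sensitivity analysis in FM cases with no other recorded condition and no regular pain medication, against the same controls. Use out-of-fold and holdout predictions. Report sensitivity and AUC, not raw accuracy, which equals w·sensitivity + (1−w)·specificity and so shifts with class mix when cases are dropped. Say beforehand what counts as maintained discrimination.
3. Word the primary conclusion as FM patients versus people with no past medical history unless discrimination is maintained in that subset.
4. Add the unequal filter to Limitations and Conclusions.

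Data Acquisition mentions intake forms but not their content. The investigator needed some history to apply the criteria, but if comorbidity and medication were not recorded, only the restricted conclusion and the added limitation are available.

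The cost is one subset analysis and some wording. The subset will be small and its estimates imprecise. Some comorbidity may be part of FM itself, so weaker performance there would not prove confounding.
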